1.4 Clinical Data to Date

This study will use data that has been collected under the following research study: "Comparative Analysis of Bile Microorganisms in Patients Undergoing Major Hepatobiliary Operations", IRB# 19-011419 and published in two peer-reviewed journals^{44,48}. In brief, these studies involved analysis of intraoperative bile aspirate samples collected from 42 patients undergoing pancreatic head resection (total pancreatectomy, n = 9; pancreaticoduodenectomy, n = 33) at Mayo Clinic, Rochester (see Table 1 for patient characteristics). Metagenomic ONT sequencing was performed on bile aspirates to identify microbial species (bacterial, fungal) and antibiotic resistance genes. Sequencing results were then compared to bile cultures performed as part of Mayo Clinic's standard of care clinical practice to determine how ONT sequencing compared to current 'Gold Standard' culture practices^{44,48}.

To determine the optimum ONT protocol for detection of microbial species and antibiotic resistance genes present in the bile aspirates, different methods of DNA extraction, use of host DNA depletion, and use of different AMR gene databases were evaluated⁴⁸. In total, intraoperative biliary microbes were detected in 54.7% (23/42) of patients undergoing total pancreatectomy or pancreaticoduodenectomy using SC techniques. This included 35.7% (15/42) of patients with positive bacterial cultures, 2.4% (1/42) of patients with positive fungal cultures, and 16.7% of patients with positive fungal and bacterial cultures. The male sex, use of biliary instrumentation, and performance of vascular reconstruction during surgery was significantly correlated with the detection of biliary microbes.

Table 1: Clinical characteristics of patients included in our preliminary study

Clinical feature	Total	Biliary microbes ⁺	Biliary microbes ⁻	P value
Age, mean (IQR)	61 (22 - 71)	66.3 (46.3 - 81.3)	58.0 (18 - 82.6)	0.0858
BMI, mean (IQR)	26.4 (19 - 40.4)	26.3 (19 - 40.4)	26.4 (19.7 - 36.2)	0.9295
Sex, % male (n)	54.8 (23)	38.1 (16)	16.7 (7)	0.0375
Surgery indication, % (n)				0.892
Pancreatic ductal adenocarcinoma	45 (29)	50 (21)	19.0 (8)	
Intraductal Papillary Mucinous Neoplasm	7.1 (3)	0 (0)	7.1 (3)	
Neuroendocrine tumors	11.9 (5)	2.4 (1)	9.5 (4)	
Other	11.9 (5)	2.4 (1)	9.5 (4)	
ASM Score, mean (IQR)	2.6 (1 - 4)	2.7 (2 - 4)	2.5 (1 - 3)	0.1874
Type of surgery				0.9716
Total pancreatectomy, % (n)	21 (9)	11.9 (5)	9.5 (4)	

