3.1 Inclusion Criteria

- ≥ 18 yr M or F
- Undergoing pancreaticoduodenectomy or total pancreatectomy for any benign or malignant indication with informed consent

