6.2 Statistical Methods

Descriptive Statistics

The primary analysis of this study will be a modified intention to treat analysis (ITT), performed to determine how use of ONT changed patient treatment, i.e. did use of ONT improve antibiotic stewardship. Proportions of patients with detection of microbes of interest will be estimated along with exact 95% binomial confidence intervals. Comparisons of the proportions between the two study arms will be compared using Fisher's exact test or Chi-square test as appropriate. We will calculate the time from randomization to first microbial detection within a patient. We will report the mean difference in time to first microbial detection within 96 hours post randomization in both treatment arms, together with a 95% confidence interval. Comparison of time to first microbial detection within 96 hours post randomization, will be performed using Wilcoxon rank sum test or two sample t-test as appropriate. If there are any baseline imbalances in demographic or clinical variables between the two groups, we will perform the analysis using univariable and multivariable linear regression adjusting for these variables with imbalances as possible confounders. Duration of antibiotics, total number of different antibiotics, and broad-spectrum antibiotics vs narrow-spectrum antibiotics administered in the two arms will be compared to determine if use of ONT improved antibiotic stewardship by significantly reducing the duration of perioperative antibiotics and use of broad-spectrum antibiotics

Secondary analysis will evaluate SSI's will be evaluated and classified using ACS NSQIP definitions and data collected will include mortality rate, SSI incidence rate, ICU length of stay, total length of hospital stay, need for interventional procedures, and hospital readmission. Statistical analysis will be performed by the study team to determine if use of ONT significantly improved patient outcome compared to patients who received standard of care

only. The secondary endpoint of the study is a binary endpoint i.e. whether patients develop SSI (yes, no). Association between the secondary outcome and predictor variables will be assessed using univariable and multivariable logistic regression.

In both primary and secondary analysis, the following variables will be assessed for inclusion in the regression models

- Age at time of surgery DOB
- BMI at time of surgery RAVE calculate
- Sex

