- Diabetes mellitus co-morbidity at time of surgery (clarifications needed for data collection)
- Cancer diagnosis
- ASA score at time of surgery
- Administration of chemotherapy prior to surgery (from what timepoint or date of last chemo?)
- Presence of biliary stent at time of surgery
- Blood loss during surgery
- Length of surgery (skin to skin, open to close?)
- Vascular reconstruction (arterial, venous) during surgery
- Closure technique
- Pancreatic leak risk score (when done? In record?)
- Surgical drains (what is needed)
- Post-op TPN

Variables with p-values less than 0.15 will be considered as potential candidates for a multivariable model. We will report odds ratios and 95% confidence interval. The area under the receiver operating characteristic (ROC) curve will be estimated as a measure of the ability of the model to discriminate between patients who had SSI within 90 days versus those who did not. An area under the ROC estimate of 0.7–0.8 will be regarded as acceptable, 0.8–0.9 will be regarded as excellent, and more than 0.9 will be regarded as outstanding.

We will also assess cost effectiveness of using ONT compared to SC. To achieve this, we will compare the cost to perform SC testing and ONT testing against costs associated with post-operative patient care. This will include the total cost to administer perioperative antibiotics, costs associated with length of hospital stay, and the costs associated with the need of additional procedures and tests associated with SSI (i.e. post-operative SC and antibiotic susceptibility testing, additional antibiotics, wound debridement, abdominal abscess drainage, CT scan, US scan).

For continuous variables, t-test will be performed and for binary variables chi-square or fisher's exact testing will be performed as appropriate. Additional analysis will be performed as necessary to determine differences in study arms. Should additional analysis beyond the scope of our abilities is necessary then a statistician will be employed.

Inpatient related costs associated with each intervention arm will be analyzed and compared with the assistance of the Robert D. and Patricia E. Kern Center for Science of Health Care in order to understand the economic impact of each intervention arm.

Handling of Missing Data

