Missing data could arise from lost samples or from a catastrophic failure of computer storage and backup systems. If any of these were to occur before an intervention could be determined using ONT sequencing, we will note these events and revert the patient to Standard of Care group.

Primary Hypothesis:

The use of ONT sequencing, a novel metagenomic technique, will result in more rapid identification of organisms in intra-operatively collected bile samples and allow for earlier treatment of biliary microbial contamination. Supplementing SC with ONT sequencing data will allow patients to be treated earlier in the post-operative setting with tailored antibiotics, which will reduce the rate of biliary microbial contamination related SSIs in patients undergoing pancreatic head resection as compared to standard cultures alone and will improve antimicrobial stewardship by avoiding unnecessary use of antibiotics.

7 Safety and Adverse Events

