8.3 Case Report Forms

A Case Report Form (CRF) will be completed for each subject enrolled into the clinical study. The investigator-sponsor will review, approve and sign/date each completed CRF; the investigator-sponsor's signature serving as attestation of the investigator-sponsor's responsibility for ensuring that all clinical and laboratory data entered on the CRF are complete, accurate and authentic.

The study case report form (CRF) is the primary data collection instrument for the study. All data requested on the CRF must be recorded. If a space on the CRF is left blank because the procedure was not done or the question was not asked, "N/D" will be entered in RAVE. If the item is not applicable to the individual case, write "N/A". All entries should be printed legibly in ink on the Source Document Worksheet.

Data Handling and Record Keeping

Confidentiality

Information about study subjects will be kept confidential and managed according to the requirements of the Health Insurance Portability and Accountability Act of 1996 (HIPAA).

Those regulations require a signed subject authorization informing the subject of the following:

- What protected health information (PHI) will be collected from subjects in this study
- Who will have access to that information and why
- Who will use or disclose that information
- The rights of a research subject to revoke their authorization for use of their PHI.

(This information is contained within the Mayo IRB Informed Consent Template Section 14) In the event that a subject revokes authorization to collect or use PHI, the investigator, by regulation, retains the ability to use all information collected prior to the revocation of subject authorization. For subjects that have revoked authorization to collect or use PHI, attempts will be made to obtain permission to collect at least vital status (long term survival status that the subject is alive) at the end of their scheduled study period.

Source Documents

Source data is all information, original records of clinical findings, observations, or other activities in a clinical trial necessary for the reconstruction and evaluation of the trial.

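### Section 6.2 offers a pancreatic leak risk score as a covariate although it has no natural value after total pancreatectomy, and leaves operation type, a stratification factor, off the list

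*Combined protocol and SAP*

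**What the plan says.** Section 6.2 introduces its covariate list with "In both primary and secondary analysis, the following variables will be assessed for inclusion in the regression models". One of the 15 entries is "Pancreatic leak risk score (when done? In record", an open drafting query about when the score is obtained and where it is held. The document gives no definition, scale or source for it. The selection rule is "Variables with p-values less than 0.15 will be considered as potential candidates for a multivariable model". For the primary analysis, regression adjustment is introduced by the condition "If there are any baseline imbalances in demographic or clinical variables between the two groups". The logistic regression for surgical site infection (SSI) carries no such condition.

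Section 3.1 admits patients "Undergoing pancreaticoduodenectomy or total pancreatectomy for any benign or malignant indication with informed consent". Section 4.2 names operation type and pre-operative biliary stenting as the two potential confounders and stratifies on both, and section 5.2 repeats this. Section 2.1 (General Design) adds age, sex and ASA score as stratification factors. Age, sex, ASA score and stenting are all on the 6.2 list; operation type is not.

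Section 8.3 has a general instruction to enter N/A for an item that does not apply to the individual case. The missing-data paragraph of 6.2 opens with "Missing data could arise from lost samples or from a catastrophic failure of computer storage and backup systems" and deals only with such losses before an ONT-guided decision. It says nothing about covariates.

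**The concern.** Total pancreatectomy removes the whole gland, so no remnant is left to leak and a remnant-leak score has no natural value for these patients. The plan does not say what to record for them or how such a record enters a model. If the entry is N/A and the model is fitted in the usual complete-case way, every total pancreatectomy patient in both arms drops out of any model that uses the score. One whole level of a stratification factor is then gone.

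This matters because the success criteria for both objectives (section 2.2, Primary and Secondary) are worded as effects adjusted for key covariates at p<0.1, while 6.2 calls its primary analysis modified intention to treat. An adjusted estimate that omits one type of operation no longer describes the randomised population. The p<0.15 screen would also judge this variable on fewer patients than the others. Because operation type is not on the list, the plan lacks the term that would let these patients stay in the model with a sensible coding.

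**Working it through.** **Inputs.** Pilot operation mix (section 1.4): "total pancreatectomy, n = 9; pancreaticoduodenectomy, n = 33", so 9 of 42. Target accrual 140 (section 3). Entry threshold p<0.15 (section 6.2). Sizing assumptions 54% v 77% detection, 80% power, alpha 0.05, 66 per group (section 6.1). Pilot SSI (section 1.4): 9 within 30 days plus 2 later, so 11 of 42.

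**1. The plan's own sample size.** Two-sided test, pooled variance, no continuity correction, mean proportion 0.655:

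n = [1.960·√(2 × 0.655 × 0.345) + 0.842·√(0.54 × 0.46 + 0.77 × 0.23)]² / 0.23² = 65.9, so 66 per group.

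This matches the stated figure.

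**2. Patients without a natural value for the score.**
- Share: 9/42 = 21.4%, exact 95% interval 10.3% to 36.8%.
- Expected number: 140 × 9/42 = 30. Range: 140 × 0.103 = 14 to 140 × 0.368 = 52.
- Remaining if all are dropped: 110 (range 126 to 88).

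**3. Precision from sample size alone.** Interval width grows by √(140/remaining).

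| Dropped | Remaining | Width factor | Power of a generic test that has 80% at 140 |
|---|---|---|---|
| 14 | 126 | 1.05 | 76% |
| 30 | 110 | 1.13 | 70% |
| 52 | 88 | 1.26 | 60% |

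The last column is Φ[(1.960 + 0.842)/factor − 1.960], for a two-sided test at 0.05. It is illustrative. For the contrast actually used for sizing (54% v 77%), power is 82.4% at 70 per arm and 72.4% at 55 per arm. That contrast is neither the antibiotic endpoint nor the SSI endpoint.

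**4. SSI events available to the logistic model.** 140 × 11/42 = 36.7 against 110 × 11/42 = 28.8, assuming the same SSI rate for both operations.

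**5. Chance that the score passes the screen for SSI.** Simulated univariable logistic fits (6,000 per setting) with 110 patients, a standardised score and 26.2% SSI at the mean score gave p<0.15 in about 14% with no association, about 65% at an odds ratio of 1.5 per SD and about 95% at 2.0 per SD. The association strengths are assumptions, because the documents give none. No comparable figure can be given for the antibiotic models.

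**6. The alternative coding.** Suppose total pancreatectomy patients were instead given a zero or lowest-risk value. Without an operation-type term, the model would treat them as the lowest-risk pancreaticoduodenectomy patients, and the score coefficient would mix leak risk with the difference between operations. With the term, all 140 stay in and the coefficient refers to pancreaticoduodenectomy only.

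**The case against.** The strongest reply is that the documents do not say these patients are excluded. A reader might infer that the CRF rule assigns them N/A and that every model using the score drops them. The text does not go that far. The rule in 8.3 is general and does not mention this score. The score is undefined and might be recorded as lowest risk, as a category, or not at all. Complete-case fitting is customary software behaviour, not a provision of the plan. All of this stands, and the loss is therefore conditional.

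The reach is also limited. The score is one of 15 variables, and those that pass the screen are only potential candidates. The primary analysis compares arms directly and brings in regression only for imbalanced variables. Section 2.2 asks for adjustment for key covariates but does not name this one. The t, chi-square and Fisher comparisons keep every patient. This stands too.

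A reader might also take the fall from 80% to 70% as a loss of the trial's power. The documents do not support that: their 80% belongs to a detection-rate contrast at N = 132, no power is stated for any adjusted model, and the success criteria use p<0.1. The 13% widening likewise ignores any residual variance that a prognostic covariate would explain.

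Finally, several other list entries carry drafting queries, so this could be seen as one symptom of an unfinished list. That is fair, but a definition and a collection time would settle most of those queries. They would not settle this one: the score would still have no natural value for one randomised stratum, and the term needed to handle that is absent.

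**Conclusion.** The concern holds in conditional form. Section 6.2 admits an undefined covariate that has no natural value for a randomised group making up about a fifth of the pilot, omits the operation-type term, and has no rule for an inapplicable covariate. If the score is recorded as N/A and models are fitted to complete cases, the screen for this variable and any model containing it lose about 30 of 140 patients (about 14 to 52). The adjusted result then describes pancreaticoduodenectomy only, with intervals about 13% wider (5% to 26%) from sample size alone.

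This rests on three assumptions: that the trial has the pilot's operation mix, for which the plan sets no quota; that the score concerns the pancreatic remnant; and that nothing written elsewhere fixes its value after total pancreatectomy. It does not show that the primary result will lose patients. The exposure is greatest in the SSI logistic regression, where the score enters through the p<0.15 screen with no imbalance condition.

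**What to change.** In section 6.2:

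1. Add operation type to the adjusted models as a stratification factor, without passing it through the p<0.15 screen.
2. Either drop the leak risk score, or define it and enter it nested within operation: an indicator for pancreaticoduodenectomy plus that indicator multiplied by the score centred among pancreaticoduodenectomy patients, so that the product is 0 for total pancreatectomy.
3. State that no randomised patient leaves an adjusted analysis because a covariate is N/A.

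The cost is one model parameter for operation type and a second if the score is kept. Dropping the score gives up leak-risk information among pancreaticoduodenectomy patients, who were 33 of 42 (79%) of the pilot. Keeping it also means answering the plan's own query about when the score is determined and where it is recorded. Operation type is already needed for randomisation, so adding it requires no new data.

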2.1 General Design

This will be a prospective 1:1 randomized controlled trial with the following study arms:

Arm 1: Patient Group 1

Standard Care Only. Patients will undergo intra-operative bile aspiration (as is routinely performed) with SC of the aspirate. All patients will receive standard prophylactic antibiotics according to practice standards and will be continued for up to 5 days as is routine. If bile cultures are positive, antimicrobials will be continued for a complete 10-day course of antibiotics (Figure 2).

Arm 2: Patient Group 2

Standard Care + ONT. Patients will undergo intra-operative bile aspiration (as is routinely performed) with standard cultures AND ONT sequencing of the aspirate. All patients will receive standard prophylactic antibiotics according to practice standards. ONT sequencing results will be made available to providers through electronic medical record (EMR) and team electronic notifications. Patients with negative ONT results will be taken off the standard prophylactic antibiotics and patients with positive ONT results will have antimicrobial therapy adjusted according to ONT sequencing results. However, if SCs are positive or suggest alternative/broader coverage then these results

will guide therapy and not ONT results. If bile cultures are positive, antimicrobials will be continued for a complete 10-day course of antibiotics (Figure 2).

[figure not shown]

Figure 2: A schematic diagram of our proposed study to investigate the use of Oxford nanopore sequencing to detect and characterize biliary microbial contamination

The study will include patients undergoing elective pancreaticoduodenectomy or total pancreatectomy for any clinical indication. Patients will be excluded from the study if they are < 18 years of age, enrolled in any similar clinical trials involving use of peri-operative antibiotics, are undergoing distal pancreatectomy, or undergoing emergency total pancreatectomy or emergency pancreaticoduodenectomy (Table 4). Following recruitment to the study, patients will be randomly assigned intraoperatively/post-operative to either the control group (Arm 1) or the interventional group (Arm 2). We will use stratified randomization with age (below 65 years vs 65 years and above), sex, operation type (pancreaticoduodenectomy vs total pancreatectomy), biliary stenting (yes vs no), and patient ASA score as stratification factors.

Table 4: Patient inclusion and exclusion criteria for the clinical trial

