Inclusion Criteria	
 • > 18 years of age • Scheduled for elective total pancreatectomy or pancreaticoduodenectomy
Exclusion Criteria	
 • < 18 years of age

	
• Emergency total pancreatectomy or pancreaticoduodenectomy• Patients scheduled for distal pancreatectomy• Women who are pregnant• Patients without the cognitive capacity to consent• Patients enrolled in similar clinical trials involving use of perioperative antibiotics
--	--

Bile will be collected via bile duct aspiration. Bile aspiration will be performed with a 16-gauge needle and 3 cc syringe prior to bile duct division (Figure 3), and aspirated material will be aseptically transferred into sterile aerobic and anaerobic transport vials. Samples will be concurrently transported to the Pathology lab and the microbiome lab to undergo SC techniques and ONT sequencing, respectively. Standardization of bile collection and surgical procedure will be assured as all surgeries will be performed by the same lead surgeon, [name]. Surgical variables that have been associated with increased SSI risk will be recorded. This will include patient sex, age, BMI, ASA score, the volume of blood loss, whether the patient had a biliary stent inserted prior to surgery, closure technique, and whether vascular reconstruction was performed during surgery.

[figure not shown]

Figure 3: Collection of intraoperative bile aspirate during pancreatic head resection (total pancreatectomy, pancreaticoduodenectomy)

SCs obtained from intraoperative bile aspiration for both study arms will be performed in compliance with clinical standards. This is routinely performed by the Pathology lab and no changes to these protocols are necessary (see Supplementary Materials S1 – S6) for culture methods and AST protocols). Results will be reported in the EMR which will be accessible by the clinical team, as is the current clinical practice. ONT sequencing for those assigned to Study Arm 2 will be performed on a 1cc liquid bile sample collected fresh from the operating room after specimen release from the Pathology lab. Approval from our institutional TRAG

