(Tissue Request Acquisition Group), will be requested for managing of intraoperative samples and will notify the study team of sample receipt. After collection, microbial DNA will be extracted and sequenced in preparation for reading per protocols^{44,48}. In brief, Porechop and BBMap will be used to remove adaptor sequences and low complexity reads. The filtered reads will then be aligned using Centrifuge in order to determine species identification. Bile aspirates will be declared microbial positive when 500 or more microbial reads are detected. Additionally, 50 reads per million (RPM) ratio (RPM-r), defined as $RPM-r = RPM_{sample} / RPM_{negative\ control}$, will be used as a minimum threshold to reduce biases caused by different sequencing depth and mitigate concerns regarding potential microbial contamination, as described in previous studies^{47,73,78,79}. Relative abundance of the microbial species detected will then be determined and high abundant species (species with a relative abundance greater than 1%) will then be reported to the care team. The sequenced reads will also be used to identify acquired chromosomal AMR genes and putative AMR phenotypes using ResFinder 4.1⁵¹. A minimum coverage of 95% and a minimum sequence identity of 95% will be used, and predicted phenotype and source organism of the identified AMR gene will be reported to the care team. To ensure that no potential resistance phenotypes are missed we will also use the PlasmidFinder and CARD tools with the default settings to check for any plasmid-acquired AMR phenotypes. This will be a critical step as CRE and ESBL genes are located on plasmids. However, due to these genes being located on plasmids, use of PlasmidFinder and CARD will not be used to declare presence of CRE- and/or ESBL-organisms but instead inform the Surgical Clinical Pharmacy and the Pathology laboratory about their potential presence in the patient sample.

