After sequencing data is gathered, samples will be destroyed. The data results from the ONT sequencing testing will be entered into EMR as a research clinic note for documentation and results will additionally be emailed to the medical providers on the care team. Decisions on antibiotic regimen will be made with the assistance of Surgical Clinical Pharmacy with changes in regimens as deemed appropriate based on standard cultures and ONT results, as described in Table 5. A negative ONT result will result in discontinuation of perioperative antibiotics after 24 hours while a positive ONT result will be used to guide early targeted antibiotic therapy (Table 5). With regards to early discontinuation of antibiotics, we are confident that this will not adversely impact patient care as our preliminary data demonstrated that ONT resulted in no false negative calls. However, as this is a new technology, SC will be performed alongside ONT, and if microbial growth is detected in the cultures, the clinician will have the option of reverting patient care to current standard of practice. This option will also be available in the event of treatment failure in patients with positive ONT results (Table 5).

Given that currently clinically available tests will be available to the care team with the additional ONT sequencing as supplemental data there will be minimal risk to subjects participating in this study.

Table 5 Incorporation of ONT results in clinical management decisions

ONT Result	Clinical management decision
A negative ONT result	Discontinue antibiotics after 24 hours of peri-operative coverage

A positive ONT result for a single pathogen typical of biliary or gastrointestinal flora	Adjust and/or narrow antibiotic therapy to cover single pathogen. If single pathogen deemed clinically insignificant (ie. lactobacillus), discontinue antibiotics after 24 hours of peri-operative coverage.
A positive ONT result for multiple pathogens	Adjust and/or narrow antibiotic therapy to cover all pathogens, excluding those deemed clinically insignificant. If all pathogens are considered clinically insignificant, discontinue antibiotics after 24 hours of peri-operative coverage.
A positive ONT result positive for rare or unexpected flora	Adjust and/or narrow antibiotic therapy to cover rare or unexpected flora, excluding those deemed clinically insignificant.

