5.3 Follow up Data Collection

Outcomes will be abstracted from the medical record for 90-days post-operatively and will include outcomes of primary endpoints that include: duration of perioperative antibiotic regimen, total number of antibiotics administered, and administration of broad-spectrum antibiotics vs narrow-spectrum antibiotics. Secondary endpoints will include SSI rate, SSI severity (superficial, deep, organ/space, bloodstream, or urine), and total hospital costs. Standard post-pancreatectomy surgical outcomes will also be collected including: total hospital length of stay (days), ICU length of stay (days), need for and type of interventional procedures, pancreas-specific complications (pancreatic leak/grade, delayed gastric emptying, and post pancreatectomy hemorrhage) hospital readmission, and death. In addition, all culture results and ONT sequencing results will be captured and compared. Additional clinical data will be gathered if deemed appropriate for outcome analysis. Patients will be assigned a study identification number at the beginning of the study to aide in securing identifiable patient information. All patient information will be stored in a secure Medidata Rave database that

will be accessed by designated study members only. Statistical analysis will be performed to compare outcomes between study arms as described in analysis section of this application.

6 Statistical Plan

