working days after the emergency occurred. Except in such an emergency, prior approval by the sponsor-investigator is required for changes in or deviations from a plan, and if these changes or deviations may affect the scientific soundness of the plan or the rights, safety, or welfare of human subjects, FDA and IRB notification in accordance with 21 CFR 812.35(a) also is required.

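### The missing-data rule can be read as moving Arm 2 patients with a lost ONT sample or result into control, and the undefined modified ITT does not rule this out

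*Combined protocol and SAP*

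**What the plan says.** The combined protocol and SAP has one missing-data rule, under Handling of Missing Data in Section 6.2. It names two causes, lost samples and a catastrophic failure of computer storage and backup. If either happens "before an intervention could be determined using ONT sequencing, we will note these events and revert the patient to Standard of Care group".

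Four other places bear on how this is read:

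- Section 2.1 General Design describes Arm 1 as "Standard Care Only. Patients will undergo intra-operative bile aspiration", with culture of the aspirate. Culture is also run in Arm 2.
- The same section says "ONT sequencing for those assigned to Study Arm 2 will be performed on a 1cc liquid bile sample". No ONT result is expected in Arm 1.
- Section 6.2 says "The primary analysis of this study will be a modified intention to treat analysis (ITT"). This is the only mention of intention to treat, and the modification is not explained.
- Section 5.3 says "Outcomes will be abstracted from the medical record for 90-days post-operatively". Its list covers antibiotic duration, number and spectrum, SSI, and hospital costs.

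**The concern.** The rule sits in the statistical plan, under a missing-data heading, and it speaks of the patient and of a group. An analyst who follows it literally would take a patient randomised to Arm 2 and count that patient in Arm 1, because of an event that can trigger the rule only in Arm 2. An analyst who takes modified ITT to mean patients with a usable ONT result would drop the same patient. A third would keep the patient in Arm 2. The text excludes none of the three, and the trial is open (Section 4.3), so the choice could be made with the arms known.

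Transfer and exclusion both leave only successfully sequenced patients in Arm 2. The comparison then describes ONT when it works, not the strategy of ordering ONT with its failures included. For the antibiotic, SSI and cost outcomes neither step is needed, because a lost ONT sample leaves those outcomes in the medical record.

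**Working it through.** **The plan's own figure.** Section 6.1 gives 66 per group for 54% against 77%, alpha 0.05 and power 80%. With pooled variance, two-sided and without continuity correction: pooled rate (0.54 + 0.77)/2 = 0.655; n = [1.960·√(2·0.655·0.345) + 0.842·√(0.54·0.46 + 0.77·0.23)]² / 0.23² = (1.318 + 0.549)²/0.0529 = 65.9, so 66. The figure reproduces. The point does not rest on it; only the target of 70 per arm is carried forward.

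**Inputs.**
- 70 per arm, 54% culture-positive, 77% ONT-positive: Section 6.1.
- Number lost in Arm 2, k: not in the documents. Assumed 2, 4 or 7 of 70 (about 3% to 10%).
- Antibiotic durations, a simplification of Section 2.1: 10 days if culture-positive, 5 if culture-negative, 1 if stopped on a negative ONT result.
- Share of Arm 2 stopping at 1 day instead of 5: either 23% (1 − 0.77) or all culture-negative patients, 46% (1 − 0.54).

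**Random loss, relative size.** Let E be the effect in sequenced patients. Lost patients get standard care and contribute no effect.
- As randomised: E·(70−k)/70.
- After transfer or exclusion: E in expectation.
- Overstatement relative to as randomised: k/(70−k) = 2/68 = 2.9%, 4/66 = 6.1%, 7/63 = 11.1%.

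If E = 0, both expressions are 0, so random loss produces no expected difference.

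**In days.**

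| Stop at 1 day | E (days) | k | As randomised | Overstatement |
|---|---|---|---|---|
| 23% | 0.23·4 = 0.92 | 2 | 0.894 | 0.026 |
| | | 4 | 0.867 | 0.053 |
| | | 7 | 0.828 | 0.092 |
| 46% | 0.46·4 = 1.84 | 2 | 1.787 | 0.053 |
| | | 4 | 1.735 | 0.105 |
| | | 7 | 1.656 | 0.184 |

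A simulation of 200,000 trials with E = 0.92 and k = 4 gives mean differences of −0.867 as randomised, −0.919 with transfer and −0.919 with exclusion.

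**Against the standard error.** Control variance is 25·0.54·0.46 = 6.21.
- E = 0.92: the Arm 2 mean is 5.4 + 1.15 + 0.23 = 6.78 and the variance is (54 + 5.75 + 0.23) − 6.78² = 14.01. SE = √[(6.21 + 14.01)/70] = 0.54 days.
- E = 1.84: the Arm 2 variance is 81·0.54·0.46 = 20.12. SE = √[(6.21 + 20.12)/70] = 0.61 days.

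At 7 of 70 lost, the shifts are 0.092/0.54 = 0.17 SE and 0.184/0.61 = 0.30 SE. At 2 of 70 they are below 0.1 SE.

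**The case against.** The best defence is that the rule concerns care. Its trigger is a loss before ONT can direct treatment, and without a result standard care is all that is left. Section 2.1 uses the same verb for care when cultures grow organisms: "the clinician will have the option of reverting patient care to current standard of practice". Section 6.2 also names an ITT-type analysis. This stands as a plausible reading. A reader might infer that the plan orders an as-treated analysis; the documents do not go that far. They do not exclude it either, since the wording refers to a group and the modification of ITT is left open.

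A reader might also infer that loss depends on bile contamination and so could create a difference when ONT does nothing. The documents do not support that. Both named causes are logistical, and nothing links either to bile status. Low yield or a failed run might be linked, but the rule does not name them.

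Third, it is tempting to say that a lost sample leaves no outcome missing. That is true for antibiotics, SSI and costs. It fails for the proportion with microbes detected and the time to first detection within 96 hours, which Section 6.2 lists under the primary analysis. There the ONT result itself is gone, so the correction has to say what replaces it.

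Finally, the effect is small and the trial is labelled a pilot. This limits the weight of the point but does not remove it.

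**Conclusion.** The point holds as an unresolved choice of analysis population, not as proof of a planned reassignment. The only missing-data rule, taken literally, moves randomised patients into control after an event specific to Arm 2, and the undefined modified ITT does not secure the care-only reading.

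The likely size is modest: a real effect is overstated by 2.9% to 11.1%, or about 0.3 SE or less. This assumes random loss of 2 to 7 of 70 and the simplified duration model; the documents give no loss rate. There is no expected false difference under no effect. It should be fixed because the correction costs almost nothing and the main outcomes are available anyway. Confidence is medium, since the sponsor may have meant care only.

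**What to change.** **Section 6.2, Handling of Missing Data.** State that a patient whose ONT sample or data are lost before a result can guide treatment receives standard care but is analysed in Arm 2, as randomised, in every comparison between arms. Report the number of such patients and the reasons.

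**Section 6.2, primary analysis.** Define the analysis set by assigned arm, with no transfer or exclusion for loss of the ONT sample or data, and say what else, if anything, the word modified covers.

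**Detection outcomes.** For the proportion with microbes detected and the time to first detection, use these patients' standard culture result, since culture is run in both arms.

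**Cost.** No new data are needed for the antibiotic, SSI and cost outcomes. The change is a protocol amendment; if it is judged to affect scientific soundness or subjects' rights, safety or welfare, Section 7.1.3 (Deviations from the investigational plan) says "FDA and IRB notification in accordance with 21 CFR 812.35(a) also is required". Keeping these patients in Arm 2 slightly dilutes the apparent ONT effect, for example by 4/70 = 5.7%. That dilution belongs to a strategy in which some tests fail. If the sponsor meant care only, the sentence simply records it.
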